4.0 Withdrawal Criteria for study programme

Whilst participating in the study, a patient's health or diagnosis may change. If this occurs during the study, the participant eligibility for the study they are in will be re-assessed. If the participant no longer meets the eligibility criteria, their data may be removed from the database. The patient will be thanked for their time, and told not to expect to be asked to participate further.

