3.0 Sensitivity to Change Study

3.1 Aim

To assess the sensitivity to change of the SAQ, for patients who initiate a new biologic treatment for their asthma.

To determine the SAQ's minimal clinically important difference (MCID).

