3.4.2 Exclusion Criteria

Patients will be excluded from the study if they are unwilling to participate

In the opinion of the physician responsible for the care of the patient, the patient has a condition, other than asthma which is significantly contributing to their respiratory symptoms, e.g. lung cancer, heart failure or severe COPD.

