3.6 Analysis

The SAQ provides two scores, the SAQ score which is the mean of all 16 domain specific items, and the SAQ-global score which is a single item score based on the SAQ-Global, which itself is based on a Borg scale [21]. Borg scales use multiple quantifiers at empirically derived points along the scale with the aim of achieving a ratio scale. In this analysis plan, the term SAQ will refer to both the SAQ score and the SAQ global score. Separate analyses will be carried out on the SAQ score and SAQ-global. Several analyses will be carried to ensure that the MCID concept is fit for purpose.

Data from 4, 8, 12 and 16 weeks will be compared to the data collected at week 0 (baseline), providing 4 change scores per patient. Patients can indicate any one of 5 levels of improvement in any of the four weeks, or, if there is no change or deterioration, up to 11 types of change. If patients report the same level of global rating of change at each of the four time points (e.g., they record 'a little better' at week 4 and 'a little better at week 8), the average SAQ change score will be calculated for that patient. This average will then be used as the SAQ change for that particular level of global rating of change. This procedure is followed so that each patient can contribute just one value to the population average of the SAQ change score at any level of global change, and which, in the case of the level of 'a little better' is used to calculate the MCID. We shall carry out three analyses to check on the validity of the MCID concept. If the checks come out positive, then the existing method of calculating the MCID (i.e., as the change in the SAQ that maps on to the global rating of change criterion of 'a little better) will be adopted.

If the checks are negative – i.e., suggesting some revision to the way the MCID concept is employed – then we will adapt the methodology in accordance with our findings.

What degree of change on the SAQ is associated with each of the 5 levels of improvement and 5 levels of deterioration on the global rating of change score?

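### Section 4.0 allows data already collected to be removed, at discretion, when a later change in health or diagnosis ends eligibility; in Part 2 this can select the analysed sample on health-related events

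*Protocol*

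**What the plan says.** Section 4.0 covers both parts of the programme and has three steps. The trigger: "Whilst participating in the study, a patient's health or diagnosis may change". The response: "If this occurs during the study, the participant eligibility for the study they are in will be re-assessed". The consequence: "If the participant no longer meets the eligibility criteria, their data may be removed from the database". The participant is then told not to expect further requests to take part. The section does not say who decides, which data are removed, whether scores recorded while the patient was eligible are kept, or whether removals are reported.

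Part 2 has this aim in section 3.1: "To assess the sensitivity to change of the SAQ, for patients who initiate a new biologic treatment for their asthma". Its outcome is set in section 3.6: "Data from 4, 8, 12 and 16 weeks will be compared to the data collected at week 0 (baseline), providing 4 change scores per patient". The first analysis there asks what SAQ change is "associated with each of the 5 levels of improvement and 5 levels of deterioration on the global rating of change score". It also compares the change at a little better with that at a little worse. The MCID is the mean SAQ change among patients who rate themselves a little better.

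Eligibility for Part 2 (sections 3.4.1 and 3.4.2) requires starting a biologic for severe asthma at GINA step 4 & 5. It excludes the unwilling and any patient who, in the treating physician's opinion, "has a condition, other than asthma which is significantly contributing to their respiratory symptoms".

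**The concern.** Eligibility criteria define who enters. Re-applying them afterwards, and removing data that were valid when recorded, makes the analysed sample depend on what happened to patients during follow-up. In a study of change in health, with a trigger worded as "health or diagnosis may change", what happened may be related to the outcome.

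Removing someone who never had severe asthma is defensible. Removing someone who was correctly enrolled and later changed is a different act, and section 4.0 treats the two alike. The discretionary wording also means that two similar patients can be handled differently, with no rule against which to check the decision.

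At stake are the mean SAQ change at each rating level, the better/worse comparison and, if the removals fall there, the MCID. Part 1 is cross-sectional (section 2.3), so the argument about change does not apply to it directly. It is touched through the Part 2 baseline data added to it (sections 3.2 and 3.5) and through any discretionary removals of its own.

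**Working it through.** **1. The plan's own figure.** Section 3.4.3 gives four groups of 25, effect size 0.3, 5% significance and 70% power. For a one-way analysis of variance with Cohen's f = 0.3, the noncentrality is N × f² = 100 × 0.09 = 9 on 3 and 96 degrees of freedom, and power is 69.2%. The stated figure reproduces. The point does not depend on it; it serves as the baseline in step 5.

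**2. Which Part 2 criteria can be lost after enrolment.**
- Starting a biologic is a baseline event and cannot be undone.
- Unwillingness amounts to the participant's own withdrawal, not a change in health or diagnosis.
- GINA step 4 & 5 could cease to hold in a patient who improves, if the criterion is re-applied. Worsening asthma does not breach it.
- The exclusion for a non-asthma condition can be met later, if such a condition arises or is newly recognised.

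This leaves two routes. One could remove patients who improve. The other removes patients with a new cause of respiratory symptoms, who may report worsening. The net direction is unknown.

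**3. Which estimates can move.** Section 3.6 works within rating levels. If a share p of a group is removed, and their mean change differs from that of the retained patients by D standard deviations, then

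full mean = (1 − p) × retained mean + p × removed mean,

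so retained mean − full mean = p × (retained mean − removed mean), a shift of p × D in absolute size. For the MCID, the group is the patients who rate themselves a little better. Removing patients who rate themselves worse leaves the MCID where it is, but thins the deterioration levels and one side of the better/worse comparison.

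**4. Scale, under assumed inputs.** The document gives neither p nor D. Shifts in SD units:

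| p | D = 0.5 | D = 1.0 |
|---|---|---|
| 5% | 0.025 | 0.05 |
| 10% | 0.05 | 0.10 |
| 20% | 0.10 | 0.20 |

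If D = 0 there is no shift. A larger sample does not remove the shift.

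**5. Numbers lost, under the same assumed shares.** Starting from 100 patients, removal of 5%, 10% or 20% leaves power of 66.6%, 63.8% or 57.9%. Starting from 125 (five sites of 25), it leaves 77.3%, 74.8% or 69.2%. Section 3.4.3 justifies the fifth site by possible under-recruitment, not by removed data.

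**6. Whether another section limits the rule.** Section 5.3 bars destruction of study records without the Sponsor's authorisation, but section 4.0 does not refer to it and the two are not reconciled. Section 5.2 requires deviations to be reported, but a removal that section 4.0 permits is not a deviation. Section 5.0 lists attrition proportions among the data held, but asks for no reasons and does not keep the scores. None of these restricts removal from the database.

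**The case against.** The strongest reply is that the rule is narrow. It needs both a change in health or diagnosis and a loss of eligibility. Within 16 weeks of follow-up, a new condition of the kind named in section 3.4.2 (lung cancer, heart failure, severe COPD) should be uncommon. In such a patient the SAQ change may no longer reflect asthma or its treatment, so exclusion has a measurement rationale. Copies of questionnaires stay in the medical file (section 3.5) and section 5.3 protects records, so removal from the analysis database need not be irrecoverable. Handling of patients who lose eligibility could also be set out in an analysis plan that is not shown.

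Much of this stands: the rule can select the sample, but need not do so, and the number affected may be small. It does not rescue the wording. A measurement rationale supports a flagged sensitivity analysis, not discretionary removal of earlier scores. An analysis plan also cannot use scores that the protocol has allowed to leave the database.

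Three stronger readings are tempting and are not supported.
- A reader might infer that patients who do badly are the likeliest to be removed. Worsening asthma breaches no criterion, and the GINA route would remove improvers.
- A reader might size the bias by deleting the poorest 5% or 10% of changers from a normal distribution, which shifts the whole-sample mean by 0.11 or 0.20 SD. Section 4.0 does not remove on SAQ score, and the MCID is not the whole-sample mean, so this cannot be expressed as a share of the MCID.
- A reader might infer that removals will be decided with the scores in view, because questionnaires are filed in the notes. The document does not say who decides or what they see; it only fails to prevent this.

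**Conclusion.** The concern holds in a limited form. Section 4.0 permits discretionary removal of data already collected after a true change in health or diagnosis, does not distinguish this from mistaken enrolment, and is not limited elsewhere in the protocol. In Part 2 it can select the analysed sample on health-related events, in either direction.

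The size of any bias cannot be established from the document. The 0.025–0.20 SD range and the power figures rest on assumed removal shares of 5–20%; the shifts also assume a difference of 0.5–1.0 SD between removed and retained patients. They show scale and do not predict what will happen. The MCID is affected only through removals among patients rating themselves a little better; other removals affect the remaining level means and the better/worse comparison. For Part 1 the consequence is confined to the shared baseline data and its own removals.

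The change is still worth making, because the protection is specific and nearly free.

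**What to change.** Reword section 4.0 so that:
- eligibility for analysis is judged as at enrolment;
- all data recorded while the participant was eligible are kept and analysed;
- records are removed only if the participant is found not to have met the criteria at enrolment, or asks for removal, and the decision on removal is made without sight of SAQ and GRCQ scores;
- any scores recorded after a loss of eligibility are flagged, and a sensitivity analysis is run with and without those participants;
- the number of removals and of later losses of eligibility is reported, with reasons.

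The flag and sensitivity analysis are needed because keeping earlier data does not settle how scores recorded after the change are used. Such scores may be few, since section 4.0 also ends further requests to take part.

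Section 4.0 should also refer to the retention rule in section 5.3, so that removal from the database and destruction of records are not confused.

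The cost is a few sentences of protocol text, a flag in the database and one sensitivity analysis. No stated sample size or power figure changes.

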5.0 Data Management for study programme

The study incorporates the following types of data, which will only be accessed by the research team:

- Quantitative data: Anonymised questionnaires, validating clinic data information;
- Routinely recorded clinic data and service use in the last 12 months;
- Recruitment data (proportions of uptake, completion and attrition).

In accordance with the Data Protection Act (2018), UHPNT information governance policy, all researchers will ensure that study participants' anonymity is maintained and data is stored securely. Study participants will be assigned a study ID number which will replace the patient's name on all data. Each centre will be given a different participant number pre-fix to use (see the table below). All data will

be password protected, stored securely and will only be accessible by researchers and authorised personnel from Plymouth University and UHPNT.

Table of participant numbers

Site	Participant number pre-fixes
Derriford Hospital	1.xxx
The Royal Brompton Hospital	2.xxx
University Hospital of South Manchester	3.xxx
Birmingham Heartlands Hospital	4.xxx
Royal Devon and Exeter Hospital	5.xxx

Anonymised electronic will be transferred to Plymouth University for analysis. It will be transferred from UHPNT to UoP by NHS email.

The sender will ensure that the NHS email encryption service is used. The University uses a secure shared drive which the study team will use to store electronic data. Printed anonymised data will be kept in project specific folders, stored in a locked cupboard in a locked room, under the responsibility of the Investigators.

After coding, the source questionnaires will be added to the patients' notes because they contain information which may be helpful to the clinical team. Patients' records are stored securely on UHPNT premises in accordance with UHPNT information security policy.

A document linking research IDs with clinical identification numbers will be created and stored within each of the patients' respective centres, anonymised data will be analysed by the SAQ team (RJ, MM, MH, JL and YW).

After the end of the study, anonymised information collected during the study will be made available to other researchers under an appropriate data sharing agreement, but it will not be possible to identify participants personally from any information shared.

5.1 Procedure for Accounting for Missing, Unused, and Spurious Data.

Questionnaires where the completion rate is < 10% will be defined as invalid, but the level of invalid data will be used to inform the development of the questionnaire (for example, individual items with large amounts of missing data will be scrutinised closely and may be amended or excluded from the future drafts of the scale). Data entry will be checked for 1 in 5 cases and more frequently if errors are found.

5.2 Procedures for Reporting any Deviation(s) from the Original Statistical Plan

Our study is not a trial. However, any additional analysis or deviations will be reported as such to the study management group and the independent study steering committee and other appropriate authorities as per GCP.

5.3 Archiving

Following completion of data analysis, the Sponsor will be responsible for archiving the study data and essential documentation in a secure location for a minimum period of 5 years after the end of the study. No study-related records should be destroyed unless or until the Sponsor gives authorisation to do so. Medical case notes containing source data or other trial-related information should be identified by a label "Keep until dd/mm/yyyy" where the date given is 5 years after the last participant's final study visit.

6.0 Regulatory Issues

The Investigator will ensure that this study is conducted in full conformity with relevant regulations, the UK Policy Framework for Health and Social Care Research (2017) and in accordance with the principles of the Declaration of Helsinki.

6.1 Ethics Approval

The CI will obtain a positive opinion from a Health Research Authority (HRA) Research Ethics Committee (REC) for the study.

The CI will also require a HRA approval letter and a Capability and Capacity e-mail statement from the local R&D office before recruitment of participant's into the study.

Any amendments to the study protocol will require review by HRA (and possibly the REC if the amendment is deemed to be substantial by the study sponsor) and will not be implemented until the HRA grants a favourable opinion for the amendment, which will also need to be reviewed and accepted by the NHS R&D department before they can be implemented in practice.

All correspondence with the HRA will be retained in the Trial Master File/Investigator Site File.

An annual progress report (APR) will be submitted to the HRA within 30 days of the anniversary date on which the favourable opinion was given, and annually until the trial is declared ended. It is the CI's responsibility to produce the annual reports as required. The CI will also notify the HRA and sponsor of the end of the study. If the study is ended prematurely, the CI will notify the REC, including the reasons for the premature termination.

Within one year after the end of the study, the CI will submit a final report with the results, including any publications/abstracts, to the HRA. The investigator will ensure that this study is conducted in full conformity with relevant national regulations and with the UK Policy Framework for Health and Social Care Research (2017). The research team will also bear in mind the principles of the Declaration of Helsinki when conducting the study.

6.2 Ethical Issues

We acknowledge the need to protect the dignity, rights, safety and wellbeing of participants taking part in this research study. Although the potential for harming participants as a direct result of being involved in the study are considered to be minimal, a contingency will be put in place, should a patient become distressed whilst taking part in the study. To begin patients will be made aware that the researchers are

not there as clinicians, but as researchers. Should any patient appear distressed as a result of completing the questionnaires, they will be given the opportunity to speak with a clinician. Should they have concerns about the conduct of the study, they will be given the contact details for the study CI and contact details for PALS, which will appear on the Patient Invitation Letter.

We appreciate the number of questionnaires patients are being asked to complete as part of the study and are keen to limit the burden of data collection. There are 41 questions in the four questionnaires taken together for part 1 of the study. Participants enrolled in part 2 of the study will not be asked to complete all five at their questionnaires at one occasion. At most they will be asked to complete three questionnaires. As part of their treatment for their asthma, patients on biologic treatments are asked to stay for at least 30 minutes following each injections so they can be monitored. The questionnaires can be completed during this time. This should take about 20 minutes.

6.3 Confidentiality

The Chief Investigator will preserve the confidentiality of participants taking part in the study and will comply with the Data Protection Act (2018). Research teams at all sites will ensure that participants' anonymity is maintained on all documents in compliance with national regulations. A privacy notice explaining how patient research data is used will be included in the Participant Information Sheet.

6.4 Indemnity

This is an NHS-sponsored research study. If an individual suffers negligent harm as a result of participating in the study, NHS indemnity covers NHS staff and those people responsible for conducting the trial who have honorary contracts with the relevant NHS Trust. In the case of non-negligent harm, the NHS is unable to agree in advance to pay compensation, but an *ex-gratia* payment may be considered in the event of a claim.

6.5 Sponsor

The study Sponsor is University Hospitals Plymouth NHS Trust (UHPNT). Selected sponsorship tasks will be formally delegated to the SAQ Team and study sites according to an agreed task allocation matrix.

6.6 Monitoring, Audit & Inspection

The study may be subject to monitoring by Universities Hospitals Plymouth NHS Trust under their remit as sponsor and other regulatory bodies to ensure adherence to GCP and the UK Policy Framework for Health and Social Care Research (2017). It's current policy that the R&D Office will monitor all studies sponsored by the Trust 30 days after approval of the study (from the date of Trust Capacity & Capability e-mail).

The research team will check completed study data collection documents for missing data or obvious errors before forms are sent to the SAQ Team. Data will be monitored centrally for quality and completeness by the SAQ Team and every effort will be made to recover data from incomplete forms

where possible. The SAQ Team will oversee data tracking and data entry and initiate processes to resolve data queries where necessary. The SAQ Team trial manager will devise a risk-based monitoring plan specific to the study which will include both central monitoring strategies and study site visits as appropriate.

7.1 Study Management Group

A Study Management Group (SMG) including the CI, SAQ Team, trial statistician and other personnel relevant to the study (e.g. clinicians, patient and Sponsor representatives) will meet regularly (usually monthly) throughout the duration of the trial to monitor progress, resolve day-to-day problems, oversee development of study documentation, monitor participant recruitment and retention, assess data quality, review budgetary issues, discuss analysis, interpret study findings, draft reports and plan dissemination of results.

8.0 Dissemination and Publication Policy

A website for the Severe Asthma Questionnaire has been established, www.saq.org.uk. This website includes various pages containing versions of the questionnaire, information about how the SAQ was developed, advice on use and scoring, publications, contact details and translation etc.

After publication, the study team will prepare a plain English summary of the study results which will be posted on a website and each PI will be notified. As soon as practicable, patients at sites involved in the study will be informed of the results.

A formal worldwide communications strategy will be developed to promote the use of the SAQ including submissions to the FDA and other regulatory bodies. We will plan to ensure that key opinion leaders are well informed and will provide resources for promotion such as slide sets.

9.0 Funding

An unrestricted non promotional grant from GlaxoSmithKline

10.0 Impact

The proposed studies will produce the SAQ which will be validated further for use in the UK:

The educational value for clinicians of understanding the impact of severe asthma on patients. The outputs of the research will demonstrate the differences in health issues for patients with mild-moderate asthma versus those with severe asthma. This will allow clinicians to ensure that the specific problems faced by patients with severe asthma are identified and can then be addressed and help patients to be referred appropriately.

In routine clinical practice in severe asthma services, having questionnaires to measure both the severe symptom burden and the burden of treatment will allow rational choices in the use of newer biological agents in severe asthma.

The choices will better reflect the patients' perspective. As this is a multi-centre study, the new questionnaire will get significant exposure to a large number of key severe asthma specialists and this will help its dissemination and adoption in clinical practice.

For research, especially in clinical trials of newer drugs, the questionnaire will allow better assessment of impacts which affect patients with severe asthma.

The questionnaire is expected to be more responsive to change. For example, if a drug allows a reduction in OCS exposure, the benefits can be more accurately measured particularly from a patient-centred perspective. In turn, if more accurate measurement of the burden of severe asthma and its treatment is performed in clinical trials, regulatory bodies such as NICE are better able to assess the true value of newer, but expensive, drugs (indeed, NICE has called for such measures to facilitate rational decisions on the use of relatively expensive therapies for patients who may benefit).

While the initial emphasis of this research proposal has been in the United Kingdom, the questionnaires are applicable to patient populations around the world as the issues confronting patients with severe asthma are similar. Where they can be afforded, novel biological agents may be used extensively globally. The questionnaires will help to identify those people who are likely to benefit from steroid sparing medications and measure the impact such medicines have on improving patient-related

outcomes. Given the enormous burden of severe asthma, it is imperative that the right measures are available to assess treatments for this group of patients.

